3. OBJECTIVES AND ENDPOINTS

Objectives	Endpoints					
Primary						
To evaluate the efficacy of INCB050465 in the treatment of participants with AIHA.	• Proportion of participants attaining a CR (defined as hemoglobin >12 g/dL not attributed to transfusion effect* and the normalization of hemolytic markers) at any visit from Week 6 to Week 12.					
	 Proportion of participants attaining a PR (defined as hemoglobin 10-12 g/dL or at least ≥ 2 g/dL increase from baseline not attributed to transfusion effect and the normalization of hemolytic markers) at any visit from Week 6 to Week 12. 					
	*No transfusion effect definition: > 1 week since last transfusion.					
To evaluate the safety of INCB050465 administered as repeat doses in participants with AIHA.	Safety and tolerability will be assessed by monitoring AEs, measuring vital signs and ECGs, and conducting clinical laboratory blood and urine sample assessments.					
Secondary						
To further evaluate the efficacy of INCB050465 in the treatment of participants with AIHA.	 Proportion of participants attaining a CR during postbaseline visits. 					
	Proportion of participants attaining a PR during postbaseline visits.					
	 Proportion of participants attaining a ≥ 2 g/dL increase in hemoglobin from baseline. 					
	Mean, change, and percentage change from baseline of hemoglobin.					
	Proportion of participants requiring transfusions.					
	Proportion of participants who achieve normalization of hemolytic markers. (Hemolysis markers: hemoglobin, haptoglobin, LDH, reticulocyte count, total bilirubin, and direct/indirect bilirubin.)					
	Change of daily usage of prednisone.					
	FACIT-F sub-scale assessment.					
To evaluate the PK effects of INCB050465.	PK endpoints: C _{max} , t _{max} , C _{min} , AUC _{0-t} , and CL/F.					
To evaluate the PD effects of INCB050465.	Change from baseline in PD markers: reticulocyte count, DAT for IgG and C3b, cold agglutinin levels, haptoglobin, total bilirubin, direct/indirect bilirubin, LDH, and complement assessment (CH50, C3, and C4).					

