5.1. Inclusion Criteria

A participant who meets all of the following criteria may be included in the study:

- 1. Men or women, aged 18 years or older.
- 2. Diagnosis of AIHA based on the presence of hemolytic anemia and serological evidence of anti-erythrocyte antibodies, detectable by the DAT as follows:
 - a. Warm: DAT positive for IgG only or IgG plus C3d
 - b. Cold (CAD): DAT positive for C3d only, with cold agglutinins of I specificity
 - c. Mixed: DAT positive for IgG and C3d, with coexistence of warm autoantibodies and high titer cold agglutinins
- 3. Participants who have disease progression after treatment with standard therapies that are known to confer clinical benefit or who are intolerant to treatment. There is no limit to the number of prior treatment regimens.
- 4. Hemoglobin 7 to 10 g/dL (as determined by local laboratory).
- 5. No evidence of a lymphoproliferative malignancy or other autoimmune-related underlying conditions (eg, systemic lupus erythematosus, Castleman's disease, Sjögren's syndrome, or other autoimmune diseases).

- 6. ECOG performance status score of 0 to 2 (see Appendix C and Oken et al 1982).
- 7. Willingness to avoid pregnancy or fathering children based on the criteria below:
 - a. Woman of nonchildbearing potential (ie, surgically sterile with a hysterectomy and/or bilateral oophorectomy OR postmenopausal, defined by last menstrual period > 12 months before screening and confirmed by FSH).
 - b. Woman of childbearing potential who has a negative serum pregnancy test at screening and who agrees to take appropriate precautions to avoid pregnancy (with at least 99% certainty) from screening through at least 93 days after the last dose of study drug. Permitted methods that are at least 99% effective in preventing pregnancy (see Appendix A) should be communicated to the participant and her understanding confirmed.
 - c. Man who agrees to take appropriate precautions to avoid fathering children (with at least 99% certainty) from screening through at least 93 days after the last dose of study drug. Permitted methods that are at least 99% effective in preventing pregnancy (see Appendix A) should be communicated to the participant and his understanding confirmed.
- 8. Able to comprehend and willing to sign an ICF.
- 9. Willingness to receive PJP prophylaxis during the study period.

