8.3.5.3. Iron Clinical Assessment

All participants will have iron assessments (iron, total iron-binding capacity, ferritin) at screening. If elevated ferritin levels are present (> 200 ng/mL in women or > 250 ng/mL in men), additional testing and follow-up recommendations will be provided to the investigator in consultation with the medical monitor. These recommendations will include evaluation of the liver (serum transaminases and MRI) and for other causes of iron overload as indicated by the participant's medical history.

Iron assessments will be repeated during the study at Week 6 if the participant has ongoing transfusion requirements during the study.

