7.2. Efficacy Parameters

A CR for a given visit is attained if the following 2 conditions are satisfied:

1. Hemoglobin ≥ 12 g/dL.
2. Last transfusion occurred > 1 week before the date of visit.

A PR for a given visit is achieved if the following 2 conditions are satisfied:

1. Hemoglobin 10-12 g/dL or ≥ 2 g/dL increase from baseline.
2. Last transfusion occurred > 1 week before the date of visit.

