7.4. Analysis of Secondary Efficacy Parameters

The secondary endpoints include:

1. Proportion of participants attaining a CR during postbaseline visits.
2. Proportion of participants attaining a PR during postbaseline visits.
3. Proportion of participants attaining a ≥ 2 g/dL increase in hemoglobin from baseline.
4. Mean, change, and percentage change from baseline of hemoglobin.
5. Proportion of participants requiring transfusions, defined as "Yes" if the last transfusion is within 7 days of the visit date and "No" otherwise.
6. Proportion of participants who achieve normalization of hemolytic markers (hemolysis markers: hemoglobin, haptoglobin, LDH, reticulocyte count, total bilirubin, and direct/indirect bilirubin).
7. Daily usage of prednisone.
8. FACIT-F subscale assessment.

All secondary endpoints will be summarized using descriptive statistics.

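### The ≥ 2 g/dL hemoglobin endpoint (SAP 7.4 item 3) has no transfusion condition, so a rise that SAP 7.2 rejects as a response can count as a success

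*SAP*

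**What the plan says.** **The endpoint.** SAP 7.4 gives item "3. Proportion of participants attaining a ≥ 2 g/dL increase in hemoglobin from baseline". Protocol section 3 has the same endpoint, "Proportion of participants attaining a ≥ 2 g/dL increase in hemoglobin from baseline", and SAP 2.2 and planned Table 2.2.3 repeat it. None of these places sets a transfusion condition or a visit window.

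**PR and CR.** In SAP 7.2, PR needs two things at a visit: "Hemoglobin 10-12 g/dL or ≥ 2 g/dL increase from baseline" and "Last transfusion occurred > 1 week before the date of visit". CR needs hemoglobin of at least 12 g/dL and the same transfusion condition.

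**Neighbouring items in SAP 7.4.** Item 5 scores a participant as requiring transfusion "if the last transfusion is within 7 days of the visit date and" as not requiring it otherwise. Item 4 is "Mean, change, and percentage change from baseline of hemoglobin", with no rule on recently transfused values. Item 7 is prednisone use, summarised by visit in Table 2.2.7.

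**Baseline.** SAP 4.1.3 takes the last nonmissing value before first dose, with no transfusion condition.

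**Steroids and new therapy.** Protocol 6.7.2 says that background prednisone should stay stable and may be tapered, and it permits short courses above 20 mg/day. SAP 10.1 removed the hemolysis markers from CR and PR. Under SAP 5.1, by-visit analyses include follow-up, during which protocol 8.9.2 collects the start of new AIHA therapy.

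**The concern.** A transfusion raises hemoglobin whether or not the drug works. SAP 7.2 recognises this and discounts hemoglobin for a week after a transfusion. Item 3 uses the same 2 g/dL threshold without that protection, and no general rule elsewhere in the SAP removes post-transfusion values. Followed as written, the plan can report a transfused non-responder as a hemoglobin success in a study with no control group.

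The plan provides for the situation: "Iron assessments will be repeated during the study at Week 6 if the participant has ongoing transfusion requirements during the study". Continued need for transfusion is also one of the Cohort 1 dose-increase criteria. SAP 10.1 says that the added interim analysis is to support publications and a possible Phase 3 plan in CAD, so the proportion may well be read outside the study report.

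A smaller, related gap concerns CR and PR. Without the hemolysis markers, they rest on hemoglobin and transfusion timing at any single visit. Prednisone use is summarised, but no analysis shows whether responses fall at visits that follow a steroid increase.

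**Working it through.** The plan's only statistical figures are the chances of seeing at least one AE at a 20% rate. They reproduce (1 − 0.8^10 = 0.8926; 1 − 0.8^15 = 0.9648) but do not bear on this point. The check is of the rules themselves.

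**Step 1: the rules at one visit.** Let b be baseline hemoglobin, h visit hemoglobin and d days since the last transfusion.

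- Item 3: h − b ≥ 2
- Item 5 Yes: d ≤ 7
- PR: (10 ≤ h ≤ 12 or h − b ≥ 2) and d > 7
- CR: h ≥ 12 and d > 7

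**Step 2: an example (assumed values).** Take b = 7.5, h = 9.6 and a transfusion 3 days before Week 8. The rise is 2.1, so item 3 is a success, item 5 is Yes, and PR and CR are not met. With d = 8, the same values meet PR.

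**Step 3: all combinations.** Take b from 7.0 to 10.0 (the entry range in protocol 5.1), h from 6.0 to 15.0, both in steps of 0.1, and d from 0 to 14. For each b, the number of h values with a rise of at least 2 is 10 × (13 − b) + 1. This runs from 61 down to 31 over 31 baselines: mean 46, and 46 × 31 = 1,426 pairs.

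| Set | Combinations |
|---|---|
| Item 3 success, d = 0–14 | 1,426 × 15 = 21,390 |
| of these, d = 0–7: neither PR nor CR | 1,426 × 8 = 11,408 |
| of these, d = 8–14: all meet PR as written | 1,426 × 7 = 9,982 |
| of the 9,982, h > 12 (also CR) | 31 × 30 × 7 = 6,510 |
| PR without item 3 success, d = 8–14 | 210 × 7 = 1,470 |

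The 210 pairs in the last row have h of 10–12 and a rise below 2: none for b ≤ 8.0, then 1, 2, … 20 for b = 8.1 to 10.0, and 1 + 2 + … + 20 = 210. The smallest such rise is zero (b = 10.0, h = 10.0). The counts show how the rules interact, not how often each case will occur.

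**Step 4: what follows.** At a given visit, every item 3 success with d > 7 meets CR or PR. Item 3 therefore adds to that combined category only visits with d ≤ 7. Because PR also counts 10–12 g/dL with no minimum rise, the PR tables cannot stand in for a transfusion-free ≥ 2 g/dL proportion.

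**Step 5: size.** Suppose k participants have their only item 3 successes within 7 days of a transfusion. The shift is 100 × k/n points. The documents do not give k; 1 to 3 is assumed.

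| n | k = 1 | k = 2 | k = 3 |
|---|---|---|---|
| 10 (Cohort 1) | 10 | 20 | 30 |
| 15 (Cohort 2) | 6.7 | 13.3 | 20 |
| 25 (all) | 4 | 8 | 12 |

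For scale, with assumed counts and exact (Clopper-Pearson) 95% intervals:

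- 3/10 = 30% (6.7–65.2) against 4/10 = 40% (12.2–73.8)
- 5/15 = 33.3% (11.8–61.6) against 6/15 = 40% (16.3–67.7)
- 8/25 = 32% (14.9–53.5) against 9/25 = 36% (18.0–57.5)

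A one-participant shift lies well inside the sampling error.

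**The case against.** The strongest reply is that item 3 is worded the same way wherever it appears and is defined in the protocol. Raw hemoglobin rise, PR and transfusion need are three separate measures, and one visit may score differently on each without error. Item 5 uses the matching 7-day cut, and Listing 2.2 shows transfusions, so affected participants can be traced. All efficacy analyses are exploratory, and the futility rule uses CR and PR only. This stands as far as it limits the consequences and favours keeping the protocol-defined proportion on display. It does not supply the transfusion-free proportion, and a check made from listings after the fact would be post hoc.

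On steroids, prednisone use is itself a secondary endpoint (item 7, Table 2.2.7). Tapering is allowed and could work against the drug. The drugs named in the exclusion criteria, including high-dose corticosteroids, are prohibited through safety follow-up apart from the permitted short courses. This narrows the gap but does not link steroid use to response.

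Four stronger readings are tempting, and the documents do not support them:

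- **Item 3 adds only post-transfusion visits to PR alone.** This holds only if PR includes visits that also meet CR, which neither document states. If PR excludes CR, item 3 also adds transfusion-free visits with hemoglobin above 12 g/dL (the 6,510 combinations above). Nor does it hold against the Week 6–12 primary PR, because item 3 has no visit window.
- **The bias always favours the drug.** A participant transfused shortly before baseline may start high and find a 2 g/dL rise harder to reach.
- **The plan expects many such participants.** The repeat iron test is conditional on ongoing transfusion needs and says nothing about numbers.
- **The primary endpoints share the flaw.** CR and PR both carry the transfusion condition.

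**Conclusion.** The point holds as a defect of definition in a secondary, descriptive endpoint. SAP 7.4 item 3 can count as a success a hemoglobin rise that SAP 7.2 disqualifies because of a recent transfusion, and nothing planned reports the transfusion-free ≥ 2 g/dL proportion. Item 4 has the same gap.

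Each affected participant moves the proportion by 10, 6.7 or 4 points (n = 10, 15 or 25). The number affected is unknown, and the net direction is not certain. No test, error rate, sample size or stopping rule changes. The conclusion assumes that item 3 is applied literally, with a success at any postbaseline visit sufficient.

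It should be changed because the correction costs little and the condition already exists in the SAP. The missing link between steroid use and CR/PR is a real but lesser gap: any such analysis needs a time interval that the documents do not give.

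**What to change.** 1. **Item 3 and Table 2.2.3.** Report as the main figure the proportion with a ≥ 2 g/dL rise at a visit more than 1 week after the last transfusion. State that a participant never transfused meets the condition and that a visit failing it counts as non-response. Keep the protocol-defined proportion, without the condition, alongside. Record the change in SAP 10.1.
2. **Item 4.** Keep all values and add a sensitivity summary that sets aside values, including baseline, within 7 days after a transfusion. Note that this exclusion can itself shift the mean, since it may remove visits of the sickest participants.
3. **Lesser addition, CR and PR.** Leave the definitions unchanged. Add one sensitivity analysis that counts as non-response any visit during a steroid dose above baseline or within a fixed interval after it, and any visit after the start of new AIHA therapy. Fix the interval in the SAP before analysis. It is an analyst's assumption: 7 days would match the SAP 7.2 transfusion rule, and 14 days would be stricter. New therapy matters mainly for follow-up visits in the by-visit tables.

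**Cost.** A SAP amendment and modest programming. Hemoglobin, transfusion and prednisone listings are already planned, and the start date of new AIHA therapy is collected. The downside of the third change is that a true responder given steroids for an unrelated event becomes a non-responder, in that sensitivity analysis only.

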Table 1: Schedule of Assessments

		Screening				Trea	tment					Follow-Up ^a	ı
Procedure	Protocol Section		Day 1	Wk 1 ± 3 days	Wk 2 ± 3 days	Wk 4 ± 3 days	Wk 6 ^b ± 3 days	Wk 8 ± 3 days	Wk 10 ± 3 days	Wk 12 ± 3 days (EOT)	Month 1 + 5 days	Month 2 ± 5 days	Month 3 ± 5 days (EOS)
Administrative procedures													
Informed consent	8.1.1	X											
Contact IRT	8.1.3	X	X	X	X	X	X	X	X	X	X	X	X
Review inclusion and exclusion criteria	5.1, 5.2	X	X										
Demography and medical history	8.1.4	X											
Prior/concomitant medications	8.1.5	X	X	X	X	X	X	X	X	X	X	X	X
Study drug accountability and assess compliance	6.5			X	X	X	X	X	X	X			
Study drug dispensing	6.1		X			X		X					
Prophylactic treatment for PJP	6.7.1.1		X	X	X	X	X	X	X	X	X	X	X
Safety procedures/assessments													
Physical examination ^c	8.3.2	Xc	X ^{c,d}	X	X	X		X		X			Xc
Vital signs ^e	8.3.3	X	X	X	X	X	X	X	X	X			X
Serology ^f	8.3.5.7	X											
D-Dimer	8.3.5.5	X				X		X		X			
Vitamin B12/folic acid	8.3.5.2	X											
FSHg	8.3.5.6	X											
Serum pregnancyh	8.3.5.6	X											
Urine pregnancy ^h	8.3.5.6		X	X	X	X	X	X	X	X			
Urinalysis	8.3.5.4	X								X			
Serum chemistries ⁱ	8.3.5.1 8.3.5.3	X	X	X	X	X	X	X	X	X	X	X	X
12-Lead ECG ^j	8.3.4	X			X			X		X			
AE assessment	8.3.1	X	X	X	X	X	X	X	X	X	X	X	X

Table 1: Schedule of Assessments (Continued)

		Screening	Treatment							Follow-Up ^a			
Procedure	Protocol Section	Days -28 to -1	Day 1	Wk 1 ± 3 days	Wk 2 ± 3 days	Wk 4 ± 3 days	Wk 6 ^b ± 3 days	Wk 8 ± 3 days	Wk 10 ± 3 days	Wk 12 ± 3 days (EOT)	Month 1 + 5 days	Month 2 ± 5 days	Month 3 ± 5 days (EOS)
Efficacy assessments													
Hematology	8.2.1	X	X	X	X	X	X	X	X	X	X	X	X
Hemolysis markers ^k	8.2.1	X	X	X	X	X	X	X	X	X	Xk	X^k	Xk
DAT and cold agglutinin levels	8.2.2	X								X			
Complement assessment (CH50, C3, and C4)	8.2.1		X							X			
FACIT-Fatigue sub-scale	8.2.3		X				X			X	X	X	X
PK plasma sampling ^l	8.4			X	Xm			Xm		X			

^m No food intake 4 hours predose and 1 hour postdose on Weeks 2 and 8.

VV-CLIN-000602 CONFIDENTIAL

^a For participants who are not eligible to enter into the extension period.

^b Dose modification.

^c Comprehensive physical examination at screening, Day 1, and EOS; targeted physical examination at all other time points.

^d Height and body weight will only be assessed at Day 1.

^e Vital signs will include body temperature, respiratory rate, blood pressure, and pulse.

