8.1.5. Prior and Concomitant Medications and Procedures

Prior and concomitant medications and procedures will be reviewed to determine participant eligibility. All concomitant medications and measures must be recorded in the eCRF, and any medication received or procedure performed within screening period before enrollment and up to the end of the follow-up period (see Table 1) will be recorded in the eCRF. The medication record will be maintained after signing the ICF to document concomitant medications, including any changes to the dose or regimen. Concomitant medications include any prescription, overthe-counter, or natural/herbal preparations taken or administered during the study period. Concomitant treatments and/or procedures that are required to manage a participant's medical condition during the study will also be recorded in the eCRF.

Extension Period

Use of concomitant medications should be monitored as described in Table 2 for participants in the extension period of the study to verify that participants are not taking any concomitant medication prohibited per Section 6.7.3.

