5. STATISTICAL METHODOLOGY

5.1. General Methodology

Unless otherwise noted, SAS® software (SAS Institute Inc, Cary, NC; Version 9.1 or later) will be used for the generation of all tables, graphs, and statistical analyses. Descriptive summaries for continuous variables will include, but not be limited to, the number of observations, mean, standard deviation, median, minimum, and maximum, and both the actual value and change and/or percentage from baseline (if available) will be analyzed. Descriptive summaries for categorical variables will include the number and percentage of participants in each category. All by-visit analyses will include the follow-up period if the data are available.

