2.2 Secondary Efficacy		
2.2.1	Summary of Participants Attaining a Complete Response by Visit	FAS
2.2.2	Summary of Participants Attaining a Partial Response by Visit	FAS
2.2.3	Summary of Participants Attaining a ≥ 2 g/dL Increase in Hemoglobin From Baseline	FAS
2.2.4	Summary of Hemoglobin by Visit	FAS

Table No.	Title	Population
2.2.5	Summary of Participants Requiring Transfusions	FAS
2.2.6	Summary of Participants Achieving Normalization of Hemolytic Markers by Visit	FAS
2.2.7	Summary of Daily Usage of Prednisone by Visit	FAS
2.2.8	Summary of FACIT-F Subscale by Visit	FAS
Safety		

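### A 7-day transfusion look-back on a 14-day visit grid leaves 30 of 84 treatment days outside every scheduled visit's view, so the secondary endpoint can miss transfusions

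*SAP*

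**What the plan says.** - **Endpoint.** Protocol Section 3 lists "Proportion of participants requiring transfusions" as a secondary endpoint and gives no look-back window.
- **SAP definition.** SAP 7.4 item 5 makes it a visit-linked flag: Yes "if the last transfusion is within 7 days of the visit date and" No otherwise. It does not say before the visit.
- **Companion rule.** SAP 7.2 requires for CR and PR: "Last transfusion occurred > 1 week before the date of visit". Item 5 reads as the complement of that condition.
- **Visits.** Protocol Table 1 schedules treatment visits at Day 1 and Weeks 1, 2, 4, 6, 8, 10 and 12, the weekly ones each ± 3 days, then monthly follow-up for participants who do not enter the extension.
- **Output.** SAP Appendix A plans one summary table, 2.2.5, "Summary of Participants Requiring Transfusions". Unlike Tables 2.2.1, 2.2.2, 2.2.4 and 2.2.6 to 2.2.8, its title does not say that it is by visit. Listing 2.2 lists transfusions.

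**The concern.** A 7-day window suits the question of whether a hemoglobin value is free of transfusion effect. Whether a participant needed transfusion over a period is a different question. When visits are two weeks apart, the same window leaves out part of every interval, and a participant can be transfused repeatedly yet be scored No each time.

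No other planned summary table counts the missed transfusions; they would be visible only in Listing 2.2. The SAP also does not say how the visit flags combine into one proportion.

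Because item 5 mirrors the CR/PR condition, it cannot act as an independent check on response. A transfusion that item 5 does not see at a visit is also one that does not block CR or PR at that visit.

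**Working it through.** The documents state no figure for this point, so there is none to reproduce. The check is a day count.

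**Inputs.** Visits at Weeks 1, 2, 4, 6, 8, 10 and 12 (Protocol Table 1), placed at Days 7, 14, 28, 42, 56, 70 and 84. Look-back of 7 days, with day 7 included because SAP 7.2 treats only more than 1 week as free of transfusion effect. Treatment is 12 weeks = 84 days; Weeks 6–12 = 42 days.

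**Rule.** Day *d* is seen if 0 ≤ *v* − *d* ≤ 7 for some scheduled visit *v*. Each visit therefore reaches 8 days, counting its own.

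**Nominal count.**
- Each 14-day gap leaves 14 − 8 = 6 days unseen, those 8 to 13 days before the next visit.
- There are five such gaps (Weeks 2–4, 4–6, 6–8, 8–10, 10–12): 5 × 6 = 30. The days are 15–20, 29–34, 43–48, 57–62 and 71–76. 30/84 = 35.7%.
- Weeks 6–12 hold three gaps: 3 × 6 = 18. 18/42 = 42.9%.
- Days 1–14: none unseen.

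**Visit windows.** With ± 3 days at each end, a 14-day gap can be 8 to 20 days and leaves 0 to 12 days unseen. Over all 7^7 = 823,543 combinations of whole-day shifts:
- Whole treatment period: 25/81 (30.9%) to 38/87 (43.7%).
- Weeks 6–12: 12/36 (33.3%) to 24/48 (50.0%).
- Up to the Week 2 visit: as many as 5 days can be unseen.

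**Other readings of the 7 days.** Strictly fewer than 7 days: 35/84 (41.7%) and 21/42 (50.0%). Two-sided, 7 days before or after: 0 and 0.

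**What this does to a participant, nominal visits.**

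| Schedule | First transfusion | Result |
|---|---|---|
| Every 14 days | Days 15–20 | 5 transfusions by Week 12, 3 of them in Weeks 6–12; No at all 7 visits |
| Every 28 days | Days 15–20 | 3 transfusions; No at all 7 visits |
| Every 14 days | Days 1–6 | 6 transfusions; Yes at Week 1 only |
| Every 21 days | any day to Day 70 | Yes at least once |
| Weekly | any day | Yes at least once |

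For example, transfusions on Days 18, 32, 46, 60 and 74 each fall 10 days before the next visit (Days 28, 42, 56, 70, 84).

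**How robust the first row is.** Assume visit days vary independently and uniformly over −3 to +3 days; the documents give no distribution. The share of visit combinations in which the two-weekly participant is still No at every visit is then 3%, 13%, 40%, 46%, 19% and 6% for starts on Days 15 to 20, a mean of about 21%.

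**Follow-up, only if Table 2.2.5 is by visit.** SAP 5.1 states: "All by-visit analyses will include the follow-up period if the data are available". Three monthly visits reach 8 days each, so 3 × (28 − 8) = 60 of 84 days (71%) are unseen with 28-day months, or 3 × (30 − 8) = 66 of 90 (73%) with 30-day months.

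**The case against.** - **The day shares are not error rates.** This stands. A reader might infer that 36% or 43% of transfusions, or of participants, are misclassified. The documents give no transfusion rate or timing, so they do not support that.
- **The all-No example needs a rigid rhythm, the right phase and near-nominal visits.** This stands, as the 3–46% range shows. Weekly schedules, and three-weekly schedules starting by Day 70, are caught at least once on nominal visits. The example shows what the rule permits, not what is typical.
- **The false responder.** A reader might infer that item 5 will create responders who are in fact transfusion-dependent. The two-weekly participant in the example does meet the CR/PR transfusion condition at Weeks 6, 8, 10 and 12 on nominal visits. However, that condition is the protocol's own, and response also needs a qualifying hemoglobin 8 to 13 days after a transfusion; nothing in the documents says how often that would occur.
- **The reading is not forced.** Item 5 omits the word before, and a two-sided window would leave no gap. That reading fits poorly with a rule about the last transfusion and with SAP 7.2; if it is meant, the text needs to say so. Item 5 also refers to the visit date without limiting it to scheduled visits, and Protocol 8.6 allows unscheduled visits at any time. These could capture some transfusions, but the SAP does not say whether they count.
- **Low consequence.** This is one of eight secondary efficacy endpoints, descriptive, in about 25 participants, with no hypothesis tests. That limits the weight of the point. A descriptive proportion should still describe what its title says.
- **The follow-up shares.** They apply only if the table is by visit, which its title does not say, so the point does not rest on them.

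**Conclusion.** The point holds as a defect of definition. Read as a backward 7-day look-back at scheduled visits, item 5 cannot see transfusions on 30 of 84 treatment days (36%; 31–44% within the visit windows) or on 18 of 42 days in Weeks 6–12 (43%; 33–50%). No other planned summary table counts them. The reported proportion can therefore understate transfusion need under an endpoint for which the protocol sets no window.

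The size of that understatement is unknown. For the proportion of participants ever counted, it should fall mainly on isolated transfusions and on 14- or 28-day schedules in phase with the visits. The conclusion assumes that day 7 is included and that unscheduled visits are not counted. A strict reading of 7 days widens the gap; a two-sided reading removes it; counting unscheduled visits could narrow it by an amount that cannot be stated.

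**What to change.** **Change.**
1. Keep the 7-day flag as the by-visit measure and as the CR/PR condition. Add the word before to item 5, and say whether unscheduled visits count.
2. Add two participant-level proportions to Table 2.2.5:
   - any transfusion from Day 1 to Week 12, in the FAS;
   - any transfusion from Week 6 to Week 12, among participants still in the study at Week 6.
3. Beside each, show the number who left before or during the interval. SAP 4.1.4 imputes nothing by default. On a full FAS denominator, someone gone before Week 6 would otherwise count as transfusion-free in the second row.
4. Label each row as per visit or per participant.

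A look-back to the previous visit is not proposed. It would span about 7, then 14, then 30 days, so visits would not be comparable.

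**Cost.** SAP wording and a little programming. No new data are needed: Protocol 8.1.5 already records "any medication received or procedure performed within screening period before enrollment and up to the end of the follow-up period", and transfusion dates are required for CR/PR and Listing 2.2. The downside is that the reported transfusion need may be higher. A footnote is also needed, because a participant can be both a responder and transfused within the interval.
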